1. INTRODUCTION

1.1 SUMMARY

People who use drugs (PWID) often experience multiple layers of stigma when they are living with HIV.¹ Stigma is defined as the social exclusion and dehumanization of individuals in an undesirable social category.² Interventions to help affected PWID living with HIV cope with the dual stigma related to HIV and substance use have not been studied specifically in this population. Among people living with HIV, stigma adversely impacts all aspects of the care cascade: timely HIV testing, diagnosis, treatment, adherence and retention in care.³⁻⁵ Among PWID, drug use may add to adverse social factors and create particular stigma vulnerability. Russia is a country where PWID and other HIV key populations are highly stigmatized and face discrimination. Furthermore, agonist treatment for opioid use disorder is illegal in the Russian Federation. People with substance use disorders and those living with HIV have to register with the local authorities for treatment. While many try to avoid registration, most PWID and people living with HIV (PLWH) are known to the authorities. Further qualitative findings suggest that in the absence of public anti-stigma campaigns in Russia, stigma reduction interventions should address internalized stigma and their determinants to help affected people cope with the dual stigma. Stigma interventions should be adapted to address not only affected people's shame and guilt, but also their felt hopelessness. These emotions and related feelings such as avoidance and fear of being rejected may negatively affect people's agency and mental health.^{7,8} We are proposing *Acceptance and Commitment Therapy* (ACT) as a potential behavioral intervention to target the emotions underlying internalized stigma and thus empower affected people. ACT has been shown to increase engagement in addiction care.⁹ Its use and efficacy to reduce stigma has not yet been explored among HIV-positive PWID.¹⁰ The objective of this study, "Stigma, Risk Behaviors and Health Care among HIV-positive Russian People Who Inject Drugs (SCRIPT)," is to implement and evaluate the feasibility of an adapted form of ACT targeted to PWID living with HIV in Russia as an intervention to reduce intersectional HIV and substance use stigma via a two-armed randomized controlled trial among 100 HIV-positive PWID. The central hypothesis is that ACT is feasible and can be delivered to decrease HIV and substance use stigma scores.

SCRIPT aims to evaluate: 1) the feasibility of ACT with a HIV-positive PWID population in Russia via measures of satisfaction with the intervention, general participation in intervention sessions, and fidelity to the intervention; 2) the impact of ACT on the reduction of HIV and substance use stigma scores, entry into HIV care, substance use frequency, and mental health.

The study's goal is to examine the feasibility of a new intervention and to compare this intervention's effectiveness of reducing internalized stigma with the current standard of care provided by civil society organizations (CSOs) in Russia.

SCRIPT proposes to study a stigma intervention specifically among HIV-positive PWID, broadening its scope to not only HIV-related, but also substance use-related stigma in this key population. By measuring the intervention's effect size on stigma variables and related behavioral outcomes in this population, we will better understand how to intervene on the phenomenon of stigma and ultimately inform the dissemination of stigma interventions in similar health care contexts.

1.2 SIGNIFICANCE

The SCRIPT study will assess the feasibility of an intervention designed to decrease intersectional internalized stigma among HIV-positive PWID. Potential results from this study in Russia should be applicable to comparable countries attempting to reduce stigma within this population.

2. OVERVIEW OF STUDY DESIGN

2.1 STUDY AIMS

SCRIPT's Specific Aims are as follows:

Aim 1: *Evaluate the feasibility of an ACT stigma intervention* compared to standard of care via a 2-armed RCT of 100 HIV-positive Russian PWID on the following outcomes:

- a. Primary: Satisfaction with the intervention at 1 month
- b. Secondary:
 - a. Participation in three intervention sessions;
 - b. Fidelity to the intervention, using the Adherence Raters' Manual for Stigma Treatment Study (Kohlenberg et al, 2004) and an intervention adherence score

Aim 2: *Measure changes in internalized stigma*

- a. Primary: HIV Stigma via the Simbayi HIV internalized shame scale at 1 month;
Substance Use Stigma via Modified Substance Abuse Self-Stigma Scale at 1 month
- b. Secondary:
 - a. Any initiation of HIV care (ART) at 6 months
 - b. Engagement in substance use care at 6 months
 - c. Change in last 30 days injection drug use at 6 months
- c. Exploratory
 - a. Depression as measured by the PHQ-9 at 6 months
 - b. Anxiety as measured by the GAD-7 at 6 months
 - c. Intersectional stigma as measured by both substance use stigma and HIV stigma scales at 6 months
 - d. Psychological flexibility as measured via the Acceptance and Action Questionnaire at 6 months

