2.7 INCLUSION CRITERIA

To be eligible to participate in the trial, participants will need to meet the following inclusion criteria:

1. 18 years old or older
2. HIV-positive
3. Current injection drug use (past 30 days)
4. Not currently on ART
5. Provision of contact information for two contacts to assist with follow-up
6. Address within 100 kilometers of St. Petersburg
7. Not enrolled in any other research studies
8. Possession of a telephone (home or cell)
9. Able and willing to comply with all study protocols and procedures over 6 months
10. Available at the specific days of the week and times that the group sessions will be occurring for the subsequent 3-4 weeks (to ensure that participants randomized into the intervention arm will be able to receive the intervention)

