3.5 SCHEDULE OF DATA COLLECTION

		Phone Screener	Screener and Baseline		ACT Sessions 1-3	1-month assessment (4 weeks)	6 month visit (24 weeks)
			In-person Screener	Baseline			
Screening	Verification of HIV and hx of IDU	X	X				
	Screening Questions	X	X				
Enrollment	Sign Informed Consent		X				
	Complete contact information/verify numbers			X			
Assessment	Baseline Study Assessment			X			
	1-Month Study Assessment incl ACT satisfaction questions					X	
	6-Month Study Assessment						X
	Interventionist Checklist				X		
Randomization	Randomization			X			
Intervention	Adverse Events			X		X	
	ACT Intervention				X		
Other	Compensate for Participation			X	X	X	X
	Provide Resource Card			X			
	Report Adverse Events			X	X	X	X
	Complete Tracking Forms		X	X	X	X	X

Control Group						
		Phone Screener	Screener and Baseline Visit		1 mo (4 weeks)	6 mo (24 weeks)
			In-person Screener	Baseline		
Screening	Verification of HIV and substance use	X	X			
	Screening Questions	X	X			
Enrollment	Sign Informed Consent		X			
	Complete contact information/verify numbers			X		
Assessment	Baseline Study Assessment				X	
	1-Month Study Assessment					X
	6-Month Study Assessment					X
	Randomization				X	
Other	Provide Resource Card				X	
	Compensate for Participation				X	X

	Complete Tracking Forms			X	X	X
--	-------------------------	--	--	---	---	---

3.5.A. VISIT WINDOWS

ACT Intervention Session Windows for Intervention Group

1st ACT Session

- Window open: 1 day post baseline
- Target date: 7 days post baseline
- Window close: 31 days post baseline
- Window length: 30 days

2nd ACT Session

- Window open: 8 days post baseline
- Target date: 14 days post baseline
- Window close: 29 days post baseline
- Window length: 21 days

3rd ACT Session:

- Window open: 15 days post baseline
- Target date: 21 days post baseline
- Window close: 36 days post baseline
- Window length: 21 days

Research Assessment Windows for Intervention and Control Group

Intervention Group 1 Month (4-week) Visit

- Window open: 16 days post first group session
- Target date: 30 days post first group session
- Window close: 90 days post first group session
- Window length: 74 days

Intervention Group 6 Month (24-week) Visit

- Window open: 151 days post first group session
- Target date: 180 days post first group session
- Window close: 240 days post first group session
- Window length: 89 days

Control Group 1 Month (4-week) Visit

- Window open: 16 days post baseline

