- Target date: 30 days post baseline
- Window close: 90 days post baseline
- Window length: 74 days

Control Group 6 Month (24-week) Visit

- Window open: 151 days post baseline
- Target date: 180 days post baseline
- Window close: 240 days post baseline
- Window length: 89 days

Windows listed above are used as guides for scheduling visits, but deviations may occur due to participant scheduling.

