5.2 FOLLOW UP ASSESSMENTS

Phone assessments will be permitted for 6 month assessments, as a last resort, for participants who are unable to come in-person. The 1 month assessment will take about 45 minutes, the final assessment at 6 months will take about 60 min.

Administered Assessment	Baseline	1-Month	6-Month
Demographics	X		
ART Use and Adherence	X	X	X
HIV Sex Risk Behaviors	X	X	X
HIV Risk Categories	X		
HIV Disclosure	X		X
HIV Stigma	X	X	X
Substance Use Stigma	X	X	X
Substance Use Daily Life Experience (SRS)	X		
Acceptance and Action (AAQ-II – SA)	X	X	X
Patient Health Questionnaire (PHQ-9)	X	X	X
Anxiety (GAD-7)	X	X	X
Partner Violence and Sexual Assault	X		
Alcohol Use: AUDIT-C	X		
Perceived Alcohol Stigma	X		
Drug Use	X	X	X
Overdose	X		X
Social Support Scale	X		X
VR-12 Health Survey	X		X
Health Care Utilization	X		X
Abbreviated PTSD Checklist	X		
Involvement with Police	X		X
[‡] Satisfaction with the Intervention		X	
*HIV Testing History	X		
^a COVID-19 testing history, risk behaviors, and perceptions			X

[‡]Intervention group participants only

*If this information is not collected at baseline, RAs will collect this information at a later study visit.

^a Not administered to all 6-month participants

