8.1 PRIMARY ANALYSES

The primary outcome for this aim is satisfaction with the intervention. We will calculate descriptive statistics for all variables at baseline and follow-up. Initial analyses will compare binary outcomes between groups using a chi-square test and comparing continuous outcomes (i.e. satisfaction scores) using two sample t-tests. Because ACT intervention is delivered in the form of group sessions, individuals within the same groups will be correlated. All analyses will use the intention-to-treat approach and analyze participants according to randomized group, accounting for intra-group correlation.

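### ART initiation at 6 months has no common counting period, and the visit anchor gives the ACT arm more time in which a start can count

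*Combined protocol and SAP*

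**What the plan says.** Sections 2.1 and 8 both name "Any initiation of HIV care (ART) at 6 months" as a secondary outcome of Aim 2. Section 2.7 requires participants to be "Not currently on ART", so everyone can contribute a start from enrolment. The table in section 5.2 schedules "ART Use and Adherence" at baseline, 1 month and 6 months.

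Section 3.5.A sets the 6-month visit. For controls it gives "Window open: 151 days post baseline" and "Target date: 180 days post baseline", closing on day 240. The ACT arm has the same day numbers on a different clock, for example "Window close: 240 days post first group session". The section then adds: "Windows listed above are used as guides for scheduling visits, but deviations may occur due to participant scheduling".

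The first ACT session has its own window from baseline: opens day 1, target day 7, closes day 31. Section 4.5 holds that session until five people randomized to ACT are available. The missed-visit text at the end of section 4.6 moves anyone who misses it to the next available group.

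On analysis, section 8.1 says: "Initial analyses will compare binary outcomes between groups using a chi-square test". It adds that all analyses follow intention to treat and account for correlation within groups. No section gives a last day on which a start counts, says that the start date is recorded, adjusts for time at risk, or says how a 1-month report of ART is used when the 6-month visit is missing.

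**The concern.** The proportion who have ever started ART can only rise with time, so the result depends on when it is read. If one arm is read later, it shows more starts even when the intervention does nothing. The plan builds in such a difference. Randomization takes place at the baseline visit (section 4.5), and both arms are at risk from then, but only the ACT arm's 6-month visit is pushed back by the wait for a group. The chi-square test named for binary outcomes makes no allowance for this.

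A second and lesser matter is what the reported rate means. With visits allowed over 89 days in each arm, a rate labelled 6 months averages rates at roughly 5 to 8 months.

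**Working it through.** **Inputs from the documents (section 3.5.A).** 6-month window: opens day 151, target day 180, closes day 240. First ACT session: day 1, 7 or 31 from baseline. Planned arm sizes: 65 ACT and 35 control (section 2.4).

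**Assumptions.** The documents give no ART start rate. I take 20% and 30% starting by day 180, a constant hazard, and the same hazard in both arms (no ACT effect).

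**1. The plan's own figure.** 240 − 151 = 89 days, as stated.

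**2. Both arms on the baseline clock.** ACT visit day = first-session day + visit day.

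| | Control | ACT |
|---|---|---|
| Earliest | 151 | 1 + 151 = 152 |
| Target, first session on day 7 | 180 | 7 + 180 = 187 |
| Target, first session on day 31 | 180 | 31 + 180 = 211 |
| Latest | 240 | 31 + 240 = 271 |

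At target dates ACT has 187/180 = 1.04 or 211/180 = 1.17 times the control arm's counting time.

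**3. False gain for ACT.** With p the proportion starting by day 180, F(d) = 1 − (1 − p)^(d/180).

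| p | F(180) | F(187) | F(211) | Gain, session on day 7 | Gain, session on day 31 |
|---|---|---|---|---|---|
| 20% | 20.0% | 20.7% | 23.0% | 0.7 points | 3.0 points |
| 30% | 30.0% | 31.0% | 34.2% | 1.0 point | 4.2 points |

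**4. Against the trial's precision.** Half-width = 1.96 × √[p(1 − p)(1/65 + 1/35)].
- p = 20%: 1.96 × √(0.16 × 0.04396) = 16.4 points.
- p = 30%: 1.96 × √(0.21 × 0.04396) = 18.8 points.

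These ignore clustering and dropout. The largest gain is 4.2/18.8 = 22% of the half-width.

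**5. Spread within an arm.** For p = 20%, F(151) = 17.1% and F(240) = 25.7%. For p = 30%, they are 25.9% and 37.8%. This is how far one person's chance of being counted moves between the earliest and latest permitted visit.

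**6. Starts known at 1 month.** If such reports were not carried forward, the expected loss would be F(30) × the proportion missing the 6-month visit. Assuming p of 20% to 40% and 10% to 30% missing, this runs from 3.65% × 0.10 = 0.4 to 8.16% × 0.30 = 2.5 starts per 100 participants.

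**The case against.** The strongest reply is that this matters little here. The trial mainly tests feasibility, ART start is a secondary outcome, and with 65 against 35 participants the artefact is under a quarter of the confidence interval half-width. That stands, and it is why the point is minor. It does not remove the point: the error favours ACT by design, and section 3 of the introduction's summary aside, section 1.1 says the trial is to measure effect size on related behavioral outcomes.

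Three stronger readings are tempting, and the documents do not support them.

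- A reader might infer that the wide window biases the comparison by itself, since 240/151 = 1.59 means 59% more counting time. That ratio is the extreme permitted contrast, around a target of day 180. If visit dates are distributed alike in both arms, both rates mix the same times and the test of no difference stays valid. Only a difference between arms biases it.
- A reader might infer that one arm will be traced later because of the extra ACT contacts. No section suggests this, and the direction is unclear: more contact could also bring ACT participants in earlier and offset part of the anchor effect.
- A reader might infer that ART starts reported at 1 month are discarded. Nothing says so. An outcome worded as any initiation naturally includes an earlier report, and section 8 includes all participants. What is missing is the rule.

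Two further cautions hold. Section 8.1 does not mention ART by name and calls the chi-square an initial analysis. The questionnaire is not among the documents, so a start date may already be collected.

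**Conclusion.** The point holds as a minor one. The outcome has no common counting period, and following section 3.5.A as written reads the ACT arm later than control, measured from randomization. With visits on target, the false gain for ACT is 0.7 to 1.0 points when the first session is on day 7, and 3.0 to 4.2 points when it is on day 31. These figures rest on assumed 180-day start rates of 20% and 30%, a constant hazard and no true effect. The day-31 figures describe a whole arm starting at the close of the session window, so they are an upper illustration within the stated windows, not an expectation.

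The spread within each arm affects the meaning of the reported rate and not, on its own, the comparison. The handling of 1-month reports is an unstated rule with a modest stake.

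**What to change.** Define the outcome as ART started within 180 days of randomization in both arms, counting a start reported at either the 1-month or the 6-month visit. Day 180 is the target in section 3.5.A. Sections 3.1 and 3.5 also call the visit 24 weeks, which is 24 × 7 = 168 days, so the text should state the chosen day. Record the ART start date if the ART section does not already do so.

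Estimate the arm difference at day 180 with a method that handles visits before day 180 and missed 6-month visits, for example Kaplan-Meier with censoring at the last assessment. Report it with a 95% confidence interval that respects clustering in the ACT groups, as section 8.1 requires; the standard Kaplan-Meier variance would not. Add a sensitivity analysis for missing 6-month visits, because people who are hard to reach may differ in their ART starts and censoring may then be informative.

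Moving both arms to one anchor would remove the built-in arm difference but leave the rate a mix of visit times. The dated outcome deals with both and moves no visits.

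The cost is at most one date item, some SAP wording and slightly more analysis work, with no extra visits or participants. The downsides are that starts after day 180 no longer count and that dates rest on recall.

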2.2 STUDY HYPOTHESIS

We hypothesize that the SCRIPT intervention, which utilizes an adapted form of ACT targeted to PWID living with HIV in Russia, is feasible and can be delivered to decrease HIV and substance use stigma scores.

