2.3 STUDY OUTCOMES

Aim 1. The primary outcome for aim 1 is satisfaction with the intervention at month 1, assessed by a satisfaction scale. Secondary outcomes are participation in intervention sessions and fidelity to the intervention, assessed via audio-recording. This will be scored with an ACT Adherence Checklist and the Adherence Raters' Manual for Stigma Treatment Study (Kohlenberg et al, 2004) to rate the recorded intervention audio recordings.

[figure not shown]
Aim 2. The primary outcome for aim 2 is measured change in internalized HIV stigma and substance use stigma at 1 and 6 months assessed by the Berger HIV Stigma Scale, the Leickness HIV internalized shame scale, the modified Substance Abuse Self-Stigma Scale, and the Acceptance and Action Questionnaire – Substance Abuse. Secondary outcomes are initiation of ART, recent (last 30 days) injection drug use frequency at 1 and 6 months, and mental health as measured by the PHQ-9 and GAD-7.

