3.6 DATA SOURCES

3.6.A QUESTIONNAIRES

Questionnaires will be administered at baseline, 1-, and 6-month study visits to collect information about participant demographics (e.g., age, gender), stigma scores, sex risks, substance use risk behaviors, care utilization, general and mental health.

3.6.B SESSION AUDIO RECORDINGS

We will audio-record all intervention sessions and will code a subset of these recordings for quality assurance and fidelity monitoring, i.e., to document adherence to the intervention study procedures.

3.6.C INTERVENTIONIST ADHERENCE CHECKLIST

Interventionists will fill out an intervention adherence checklist to document the items of the intervention that were covered (i.e. specific metaphors, emphasis on homework, etc.)

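### Feasibility is hypothesised without any criterion, and the test named for its primary outcome, satisfaction, has no control data to run on

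*Combined protocol and SAP*

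**What the plan says.** Section 1.1 states: "The central hypothesis is that ACT is feasible and can be delivered to decrease HIV and substance use stigma scores". Section 2.2 repeats this as the study hypothesis, that the intervention "is feasible and can be delivered to decrease HIV and substance use stigma scores", and section 2.4 says the trial sets out to test feasibility.

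Feasibility is Aim 1. Section 2.3 says: "The primary outcome for aim 1 is satisfaction with the intervention at month 1, assessed by a satisfaction scale". It continues: "Secondary outcomes are participation in intervention sessions and fidelity to the intervention, assessed via audio-recording". Section 2.1 lists the attendance outcome as "Participation in three intervention sessions". For fidelity, section 3.6 says the team "will code a subset of these recordings for quality assurance and fidelity monitoring", without giving the size of the subset or how it is chosen.

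On analysis, section 8.1 says: "The primary outcome for this aim is satisfaction with the intervention. We will calculate descriptive statistics for all variables at baseline and follow-up". It then says: "Initial analyses will compare binary outcomes between groups using a chi-square test", with two-sample t-tests for continuous outcomes and satisfaction scores given as the example. It adds that analyses follow intention to treat and allow for correlation within session groups.

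The assessment table in section 5.2 carries a footnote that restricts the satisfaction items to the intervention group. The schedules in section 3.5 agree: satisfaction questions appear in the month-1 assessment of the intervention schedule and not in that of the control schedule.

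**The concern.** A hypothesis that something is feasible needs a statement, made beforehand, of what result would support it and what would not. Here the satisfaction scale has no name or range. No attendance share and no fidelity score are set as targets, and section 8 gives no significance level or confidence level.

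The one inferential analysis tied to the Aim 1 primary outcome compares two arms, but only one arm supplies data. Controls do not have low satisfaction scores; they have none. Aim 1 therefore has no workable test and no mark against which to read its estimates. What is at stake is the credibility of a feasibility conclusion that answers the trial's first-named aim.

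**Working it through.** **1. Can the named test be run?** Set the sections side by side.

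| Aim 1 outcome | Data in ACT arm | Data in control arm | Criterion stated |
|---|---|---|---|
| Satisfaction (primary) | Yes, month 1 (5.2) | None (5.2 footnote) | None |
| Participation in three sessions | Yes | No sessions offered (3.4) | None |
| Fidelity | Yes, subset of recordings, plus checklist (3.6) | No sessions to rate | None |

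The two-sample t-test in 8.1 needs satisfaction scores from both arms. It has them from one.

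**2. Can a target be recovered from the sample size?** The plan's figure is 100. The arithmetic agrees with itself: 13 groups × 5 = 65 (2.4, 3.1), and 65 + 35 = 100 (2.4). No power, significance level, effect size, standard deviation, target rate or dropout is given, so 100 cannot be reproduced and no implied pass mark can be worked back from it.

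**3. What do descriptive statistics leave open?** Take two possible attendance results with exact 95% intervals:
- 33/65 = 50.8% (38.1% to 63.4%)
- 59/65 = 90.8% (81.0% to 96.5%)

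No written rule treats these differently.

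**4. How much does a mark chosen later matter?** Assumptions: 65 participants in 13 groups of 5, a true completion share of 60%, and an intra-group correlation (ICC) of 0 to 0.10. Group counts are binomial (ICC 0) or beta-binomial. The chance that the observed share meets the mark is:
- 50% mark (at least 33/65): 92–95%
- 60% mark (at least 39/65): 55%
- 70% mark (at least 46/65): 5–8%

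**5. Could this design support a rule?** Illustration only, with an assumed attendance floor of 50% and a one-sided 95% lower bound. Design effect DE = 1 + (5 − 1) × ICC; effective n = 65/DE. The lower bound for x attenders is the 5th percentile of Beta(x/DE, 65/DE − x/DE + 1), which is the Clopper-Pearson bound on effective counts.

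| ICC | DE | Effective n | Bound just below cut-off | Bound at cut-off | Passes if true share 70% | Passes if true share 50% |
|---|---|---|---|---|---|---|
| 0 | 1.0 | 65 | 39: 0.491 | 40: 0.506 | 95% | 4.1% |
| 0.05 | 1.2 | 54 | 40: 0.495 | 41: 0.510 | 89% | 3.5% |
| 0.10 | 1.4 | 46 | 41: 0.4997 | 42: 0.515 | 82% | 2.9% |

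Pass rates come from simulating 13 groups of 5. If the unadjusted cut-off of 40 were kept when groups are correlated, the pass rate at a true 50% would be about 6% (ICC 0.05) or 7% (ICC 0.10). This is why the bound must allow for session group.

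**6. Precision for satisfaction.** The 95% half-width in SD units is 1.96 × √(DE/n). For n = 65 it is 0.24 (ICC 0) to 0.29 (ICC 0.10). With 50 responders (assumed), keeping the same design effect, it is 0.28 to 0.33.

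**The case against.** The strongest reply is that this is a pilot, and a pilot may properly estimate feasibility without a pass mark or significance level. That stands as a matter of design: estimates with intervals would be enough. It does not rescue this text, which states feasibility as a hypothesis, says it will be tested, and names a test that lacks half its data.

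Three stronger readings are tempting, and the documents do not support them.

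- A reader might infer that no Aim 1 result could ever count against feasibility. Section 8.1 plans descriptive statistics, so poor satisfaction or attendance would be visible and could be judged informally. What is missing is a rule fixed beforehand. The stigma half of the hypothesis also has a control arm and can be contradicted.
- A reader might infer that attendance will be tested by chi-square against controls who have no sessions, so that even poor attendance would come out significant. Section 8.1 assigns chi-square to binary outcomes in general. It does not assign it to participation, and no section defines participation as binary.
- A reader might infer that dissemination plans hang on the feasibility verdict. Section 1.1 ties dissemination to effect sizes on stigma and related behaviours, which belong to Aim 2.

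It is also fair to say that the floor and the true shares used above are assumptions. They show that the choice matters, not what it should be.

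**Conclusion.** The point holds in this form: feasibility is hypothesised with no criterion for satisfaction, participation or fidelity, and the analysis named for the Aim 1 primary outcome cannot be carried out on the data the protocol collects. Followed as written, Aim 1 yields descriptive statistics only, and a claim of feasible would use a standard set after the results are known.

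The first part rests on the absence of any such criterion from the public text; section 8 shows no redaction. The second rests on a direct conflict between 8.1 and 5.2 and needs no assumption. The numerical illustrations assume 65 participants in groups of 5, an ICC of 0 to 0.10, and the stated true shares and floor.

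The sponsor should correct this, but it does not affect safety or the Aim 2 comparison. The essential gap is the mark; a significance level matters only if feasibility is tested rather than estimated.

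**What to change.** In section 8.1, remove the between-arm comparison for Aim 1. Replace it with ACT-arm estimates and confidence intervals that allow for session group:

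- mean satisfaction among month-1 responders, on a named scale with its range, reported with the response rate;
- the share of all participants randomised to ACT who attend all three sessions, stating whether the individual make-up second session (described under Missed Visits) counts.

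Then choose one of two routes.

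(a) Before any Aim 1 data are summarised, fix a sponsor-justified mark that the lower confidence bound for mean satisfaction must exceed, with supporting marks for attendance and fidelity. State how the recordings to be rated are selected. As an illustration, a 50% attendance floor would require at least 40, 41 or 42 of 65 at an ICC of 0, 0.05 or 0.10. The sponsor should choose and justify its own figure.

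(b) Delete feasibility as a hypothesis in sections 1.1 and 2.2, align the wording of 2.4, and report the estimates without a verdict.

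Either route costs a few sentences, with no added participants, visits or data. The price of (a) is that the trial can fail its feasibility criterion, and that allowing for session group lowers the chance of passing (in the illustration, from 95% to 82% at a true share of 70%). The price of (b) is giving up a formal feasibility conclusion.
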